Testing the Efficacy of FFC-AC-EIT in Patients with Alzheimer's Disease and Related Dementias

NCT04235374

Date: 1/20/2019

Protocol

Design: To achieve our Aims we will use a cluster randomized clinical trial randomizing hospitals to prevent treatment contamination that might occur if we randomized units or patients within units.

Sample and Setting: Twelve hospitals (six in Maryland and six in Pennsylvania) will be randomized to treatment (FFC-AC-EIT) or Education-Only (EO) using permuted-block randomization and 50 patients per hospital will be recruited (total 600 participants). The hypotheses for Aim 1 efficacy testing include: Patient level: **Hypothesis 1:** At discharge, hospitalized patients with ADRD on units in which FFC-AC-EIT is implemented will increase time in physical activity; maintain or improve function; perform more function focused care activities; have less incidence and severity of delirium; have less evidence of BPSD; have less pain; have fewer falls; have fewer tethers; and shorter length of stays compared to those exposed to EO; **Hypothesis 2:** Patients on units in which FFC-AC-EIT is implemented will maintain or increase time spent in physical activity; maintain or improve function; have less incidence and severity of delirium; have less evidence of BPSD; have less pain; and have fewer falls; fewer emergency room visits; fewer unplanned re-hospitalizations; and fewer new admissions to long term care at 1, 6 and 12 months post discharge when compared to those exposed to EO.

Randomization Plan: The level of engagement required for the intervention prevents random assignment at the patient level as patients could become aware of differential treatment within the same unit in the same hospital and there is the risk of carry-over of treatment by staff. Thus, after hospitals are recruited they will be randomized to cohort (See Study Timeline) and randomly assigned to treatment so that the hospital will receive either FFC-AC-EIT or EO. Random assignment will be completed by the statistician using SAS proc plan which allows for simultaneous randomization on multiple dimensions (time and hospitals). In prior research we noted no differences in implementation of function focused care based on facility related factors^{111,137}. We recognize, however, that hospital differences may exist and will be controlled for in the analysis (e.g.,bed size, ownership).

Sample Size: Sample size calculation was based on prior research and our primary focus which is on physical activity and function 12,14,15,33,106. For primary patient level outcomes, function based on the Barthel Index resulted in a Cohen's d=.24, for physical activity the Cohen's d=.37, and for participation in function focused care by patients Cohen's d=.31. The impact on tethering, a secondary outcome, was noted to have a Cohen's d=.61. Given a two-tailed alpha of .05, an estimated intra-class correlation coefficient (ICC) between clusters (hospitals) of .02, a correlation coefficient between repeated measures of .60, and assuming even dispersion of means, a total sample of 360 patients will provide sufficient power (>.80) to detect a small effect size (d=.24)¹³⁸ in primary patient level outcomes. Our prior research showed an attrition rate of 5-40% over a 12- month period. Therefore, we anticipate that a total of 600 patients from 12 hospitals (50 patients per hospital) will be sufficient to demonstrate outcomes. With regard to hospital level outcomes, our prior work resulted in effect sizes of 0.9 for environment and policy changes 15,33,106,139. With the proposed sample size of 12 hospitals the statistical power for these measures will be adequate (.90 for both outcomes based on our analysis plan).

Settings: Hospitals will be invited to participate if they: (a) have at least one unit dedicated to general medical patients; (b) identify two registered nurses (RN) to be champions (one for day and one for evening shifts); (c) enable staff to access email and websites via a phone, tablet or

computer; and (d) do not have a geriatric program (e.g., Acute Care for Elders, Hospital for Elder Life Program/ HELP) on the study units. We will implement FFC-AC-EIT in 6 hospitals (on the medical unit) and EO in 6 hospitals (on the medical unit) across Maryland and Pennsylvania. (See support letters and Facilities and Resources section).

Patient Participants: Patients will be eligible to participate if they: (a) are admitted into the hospital from any setting during the 12 month implementation period; (b) are 65 years of age or older; (c) are admitted onto a medical unit for any medical diagnosis; and (d) screen positive for dementia based on two well-validated scales: a score of ≤ 25 on the Montreal Cognitive Assessment (MoCA) and a score of >2 on the AD8 Dementia Screening Interview¹⁴⁴¹-¹⁴³; have mild to moderate stage dementia based a score of 0.5 to 2.0 on the Clinical Dementia Rating Scale (CDR)¹⁴⁴; and lastly to differentiate between dementia and mild cognitive impairment eligibility is based on evidence of functional impairment with a score of 9 or greater on the Functional Activities Questionnaire (FAQ)¹⁴⁵. The AD8, CDR and FAQ are all completed by an informant and all screening measures are reliable and valid and accurately differentiate those with and without dementia. Patients will be excluded if they: (1) are enrolled in Hospice; (2) have been on the unit for greater than 48 hours; (3) do not have a family member/caregiver that we can contact; (4) anticipate surgery; or (5) have a major acute psychiatric disorder, or significant neurological condition associated with cognition other than dementia.

The intervention activities continue for a 12 month period and we will recruit patients from the units starting at intervention month 3 and following completion of steps 1 and 2 of FFC-AC-EIT (following evaluation of the environment and policies and staff education) and following education in the EO settings. In prior research we have noted changes in staff behavior following the first two months of implementation of function focused care approaches^{39,111,115,130} therefore we initiate recruitment following this implementation period. We will obtain information about eligible patients from a designated staff member and will recruit 50 patients over the remaining 10 months of the 12 month intervention. We estimate that approximately 7 to 8 patients per week will be eligible for the study. Based on our past recruitment activity^{12,14} we will be able to enroll 1-2 patients per week which will meet our goal of approximately 5 patients per month. This will assure that patient recruitment is spread over the entire intervention period and is similar across all settings. Participants will be evaluated to determine their ability to self-consent using the Evaluation to Sign Consent questionnaire¹⁴⁶. If they do not correctly respond to all five questions, verbal or written assent will be obtained and the Legally Authorized Representative will complete the consent process (see Human Subjects section).

The Implementation of FFC-AC-EIT:

FFC-AC-EIT is implemented by a Research Nurse Facilitator working with the stakeholder team and unit champions for 10 hours weekly during months one and two and then for four hours weekly starting in month three for a total of 12 months. Timing of the intervention activities will be flexible based on the needs of the unit (e.g., times that work best for champions and Research Nurse Facilitator to meet). The first meeting with the stakeholder team will be 1-2 hours and the remaining meetings will be approximately 30 minutes monthly to update the stakeholders on progress and any challenges associated with implementation of FFC-AC-EIT (Table 1). The majority of the time on the unit by the Research Nurse Facilitator will be spent with the champions helping and assuring that they are engaging staff in function focused care activities via the four steps of FFC-AC-EIT (Table 1). Once hospitals are randomized we will set up a time to meet with the identified contact to determine the stakeholder team members and champions and organize the first stakeholder team meeting. All FFC-AC-EIT related activities will be coordinated during scheduled working hours for the stakeholders. The first meeting will provide an overview of the implementation of Steps 1 to 4 [(1) Environment and Policy

Assessments; (2) Education; (3) Establishing Patient Goals; and (4) Mentoring and Motivating of Staff, Patients and Families] and will address the unit challenges to implementing function focused care using a Brainstorming approach (Table 1). Brainstorming involves having stakeholders identify the challenges to engaging patients with ADRD in function focused care activities during their hospital stay. We then complete Affinity Diagramming by clustering the ideas identified during brainstorming into themes. Once themes are developed, an Interrelationship Diagraph will be made to determine which of the identified themes is the best or strongest driver. Drivers are established by having participants consider how each theme is connected to the other themes. For example, does staff knowledge about BPSD influence function. The theme with the most arrows going away from it is referred to as the "driver" or root cause. If there are multiple themes with the same number of arrows going out of them, they can be considered as equally important. The best driver, or the root cause, is the theme that is most likely to have an impact on why function focused care approaches are not implemented on the unit and will guide the stakeholder group in goal identification.

Table 1: Content for First FFC-AC-EIT Meeting With the Stakeholder Team

Table 1: Content for First FFC-AC-EIT Meeting With the Stakeholder Team	
Introduction and	a. Overview of project; b. Roles and responsibilities of research and stakeholder teams; c.
Overview of FFC-	Background support for FFC-AC-EIT: 1. Review of current care practices/philosophies of
AC-EIT	care; 2. Task and disease focused versus patient focused care; 3. Optimizing function and
	physical activity in acute care: identification of and solutions to challenges identified; d.
	Evaluation of the multilevel context that influences implementation of FFC-AC-EIT per unit,
	Brainstorming Activity to identify unit drivers and unit goals.
Implementation of	a. Training to complete Step 1 Environment and Policy Assessments: Review of the
Steps 1 and 2 in	Environment and Policy Assessments (Appendix A): Assessments are used to identify need
the four step	for changes in environments and policies to optimize function and safe physical activity of
process	patients with ADRD (e.g., open areas for walking). Introduce as policy the use of the Mobility
	Screen and Nursing Progressive Mobility Tool to guide nurses in setting patient goals; b.
	Training to complete Step 2 Education: Review educational materials for staff, patients as
	relevant, and families, which have been developed by the research team 12,15 and establish a
	plan for staff education sessions that will assure optimal staff participation (e.g., webinar,
	face to face). Developed education materials include powerpoints and printed materials for
	staff training, patients (as relevant) and families/caregivers about optimizing function and
	physical activity during hospital and post hospital periods.
Implementation of	a. Training to complete Step 3 Establishing Patient Physical Activity Goals: 1.
Steps 3 and 4 in	Demonstration of use of the Mobility Screen and the Nursing Progressive Mobility Tool ^{149,150} .
the 4-step process	These tools have established evidence of reliability and validity and have been used
	previously to establish patient goals ^{149,150,151} . 2. Demonstrate goal development for patients
	using the Mobility Screen and the Nursing Progressive Mobility Tool and discuss ways for
	staff to help patients achieve goals (e.g., provide chairs in the rooms; age appropriate
	weights; cueing; use of recreation activities that encourage physical activity); b. Training to
	complete Step 4 Mentoring and Motivating Staff, Patients, and Families: 1. Review self-
	efficacy techniques (e.g., verbal encouragement) that are effective for patients with ADRD
	and staff; 2. Demonstrate for champions how to complete the Nurse Checklist for Function
	Focused Care and direct them to complete this with nurses at 0-2, 4-6, and 10-12 months
	post implementation of FFC-AC-EIT and provide feedback to the nurse (e.g., positive
	reinforcement; education); review plans to view and use weekly email Tidbits which are
	innovative ideas emailed about ways to engage staff and patients in function focused care
	activities, ways to prevent and manage delirium and BPSD.
Summary of	a. Discussion of ways the stakeholder team will work with the champions and Research
Training Day	Nurse Facilitator and establish times for monthly meetings; c. Opportunity for questions; d.
	Review of timeline of project.

In the first two months the Research Nurse Facilitator completes the environment and policy assessments with the champions and implements appropriate changes on the units (e.g., clearing hallways and making them pleasant and safe, assuring that there are places to sit in the rooms) and plans and provides staff education and makes available information for patients and families/ caregivers. The education reviews function focused care, the benefits of physical activity for patients with ADRD, ways to evaluate, prevent, and manage delirium and BPSD, focuses on elimination of entrenched and inaccurate practices such as unnecessary tethering of

patients with pulse oximetry⁹⁷, completion of the Mobility Screen and establishment of patient physical activity goals using the Nursing Progressive Mobility Tool, and use of motivational techniques to engage patients with ADRD in physical activity during all care interactions without exacerbating BPSD. Ongoing work between the champions and the Research Nurse Facilitator focuses on motivating staff and patients to work toward achievement of patient goals and established unit goals.

The stakeholder team will continue to meet with the Research Nurse Facilitator monthly (approximately 30 minutes) over the 12-month intervention period to review progress and to help champions overcome any identified multilevel challenges (Figure 1). We will keep minutes of these meetings to describe the implementation process on the unit in each hospital. This cyclic feedback pattern of review of progress and challenges will help guide staff intervention activities to best respond to contextual changes on the unit and in the hospital over time. In addition to monthly visits, weekly emails containing motivational Tidbits will be sent to all stakeholder team members within the cohort. The Tidbits include such things as: updates about benefits of engaging patients with ADRD in physical activity while hospitalized; information to support de-implementation of entrenched and inaccurate practices(e.g., support for removal of tethers)97,98,152; symptom management (e.g., management of pain and BPSD); prevention and identification of delirium; motivation techniques such as using patients' prior work life or leisure activities to serve as a source of motivation to engage in physical activities 153; and motivational contests for nurses (e.g., reward for the nurse who provides the most innovative approach to engaging a patient in bathing, dressing, or ambulating). To further facilitate implementation we will give each treatment site: 1) a 100 dollar gift certificate from Nasco (Nasco.com) to buy supplies for the unit to engage patients with ADRD in physical activities (e.g., age-appropriate weights; soft horseshoe toss game); 2) 1000 dollars at the end of the study for each champion to attend a conference and submit an abstract focused on optimizing function and physical activity of hospitalized older adults with ADRD.

Education Only (EO) Control Intervention: Hospitals randomized to EO will be provided with an in-service for nursing staff on function focused care in patients with ADRD by an EO Research Nurse Facilitator using our developed PowerPoint presentations in 30-minute sessions as is currently done in usual practice. We will provide the education in the preferred format (e.g., face-to-face; webinar). No further interaction with the staff or the units will occur. We recognize that there will be differences in time exposure to the Research Nurse Facilitators but we are deliberately testing two different approaches to implementation of function focused care on hospital units with older adults with ADRD (FFC-AC-EIT versus EO). Time/exposure to the Research Nurse Facilitators is part of the approach and we will consider exposure time differences between the treatments.

Hospital descriptive data: The following data will be obtained at baseline to describe the hospitals and consider confounders: state; bed size; ownership status; urban or rural; Magnet[™] Status; teaching status.

Unit descriptive data: We will obtain staff/patient ratios and mix (registered, licensed practical nurses, and nursing assistants) at baseline, 6, 12 and 18 months and bed size.

Patient descriptive data: Data will include age, race, sex, cognitive status based on the MoCA^{140,141}, marital status, education, admission diagnosis, admission living situation, the Cumulative Illness Rating Scale (CIRS)¹⁵⁴, medications, length of stay, and discharge location and living location at each follow up period.

Measures for Aim 1 (Appendix A): Bolded measures are based on subjective data from informants (nurse/family); other measures are completed by evaluators based on observation or

chart abstracting. Environment and policy assessments are completed by evaluators who are blind to randomization.

Efficacy Data (see hypotheses 1-5 above):

For patients: Barthel Index (BI)¹⁵⁵ will be used to evaluate function. The BI is a 10 item measure of ability to perform activities of daily living (e.g., bathing, dressing) with evidence of internal consistency (alpha coefficients .62-.80), inter-rater reliability (r=.89) and validity based on correlations with the Functional Inventory Measure (r=.97)¹⁵⁵. Items are weighted to account for the amount of assistance required. A total score of 100 indicates complete independence. The Physical Activity Survey 33,156 is a subjective measure of time spent in physical activities over 24 hours based on input from an informant. Activities include locomotion (e.g., walking, wheelchair mobility), personal care (e.g., bathing), structured exercise (e.g., physical and occupational therapy), recreational activity (music), and repetitive behavior (moving objects repeatedly). Prior use of the measure provided evidence of criterion-related validity (r=.55 -.60. p<.05) and inter-rater reliability (r=.82 -.94, p<.05)^{33,156}. The MotionWatch 8 (only obtained during hospitalization) is a compact, lightweight, wrist-worn activity monitoring device used to document physical movement. The MotionWatch 8 contains a miniature accelerometer to allow measurement and recording of physical movement of the wrist which provides a close correlation to whole body movement. Reliability, validity, and cutpoints for different levels of activity have been established for older adults 157. We will place the MotionWatch 8 on at baseline and leave this on till discharge so that we can capture baseline activities (the first 24 hours of measurement), mean daily activity while hospitalized and discharge activities (the 24 hours prior to discharge). Specifically we will collect counts of activity and time spent in sedentary, moderate, and vigorous activity during these time periods. Patient Checklist for Function Focused Care (only completed during hospitalization) is a 19-item measure in which nurse-patient interactions are evaluated over a 30 minute period to determine if the patient performs function focused care (e.g., participates in bathing at his or her highest level). Patients either do or do not perform the activity (e.g., patient refuses to perform). If the item/activity is not observed it is marked as not observed. Percentage scores are calculated based on function focused care performed/observed activities. Prior testing supported inter-rater reliability (r = .92) and validity based on correlations with function $(r = .89)^{158}$. Delirium occurrence will be based on structured interviews consisting of questions from the MoCA^{140,141} first to establish if there is evidence of cognitive impairment and then the Confusion Assessment Method (CAM) to establish if there is delirium¹⁵¹. A review of studies testing the psychometric properties of the CAM noted that in seven high quality studies there was an overall sensitivity of 94% (95% confidence interval, CI, 91-97%), and specificity of 89% (95% CI, 85-94%)¹⁵⁹ and evidence of inter-rater reliability 160. Delirium severity will be determined based on the **Delirium Rating Scale** which is a 10 item scale that is completed by an informant¹⁶¹. Prior testing supported the validity of this measure based on differentiation of delirium among different groups of patients and reliability based on inter-rater reliability (r=.97). Scores can range from 0-26 with higher scores indicative of more severe delirium. BPSD will be evaluated using the **Brief Neuropsychiatric** Inventory (NPI-Q)¹⁶² which is a 12-item, reliable and valid informant-based assessment of neuropsychiatric symptoms. Each of the 12 NPI-Q domains contains a survey question that reflects symptoms of that domain and if present then severity is rated (symptoms include resistance to care, apathy, anxiety, depression, motor disturbance, disinhibition, agitation, sleep issues, hallucinations, and delusions). The informant (nurse/caregiver) providing care to the patient on the day of testing will be asked to respond to the items based on the past 24 hours. Prior testing has established evidence of validity of the measure with a sensitivity of 74% and specificity of 80% and test retest reliability (r=.99)¹⁶³. Pain will be evaluated using the *Pain* Assessment in Advanced Dementia (PAINAD)¹⁶⁴. The PAINAD includes 5 behaviors that are

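### Patients are identified after hospitals are randomised, through staff who very probably know the arm, and no rule sets which of the many eligible patients are approached, so the arms can differ by selection

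*Combined protocol and SAP*

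**What the plan says.** **Order of events.** Under Randomization Plan, "after hospitals are recruited they will be randomized to cohort" and assigned to FFC-AC-EIT or Education-Only (EO). Patients come later. The recruitment paragraph that follows the eligibility criteria (Patient Participants) states that "we will recruit patients from the units starting at intervention month 3 and following completion of steps 1 and 2 of FFC-AC-EIT", with EO hospitals starting after their own education. The reason given is that "In prior research we have noted changes in staff behavior following the first two months of implementation of function focused care approaches".

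**Source of patients.** "We will obtain information about eligible patients from a designated staff member". That person's role, and whether they know the allocation, are not stated.

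**Numbers.** "We estimate that approximately 7 to 8 patients per week will be eligible for the study". The team "will recruit 50 patients over the remaining 10 months of the 12 month intervention", and expects that "we will be able to enroll 1-2 patients per week which will meet our goal of approximately 5 patients per month". The plan concludes that recruitment will be spread over the period and similar across settings.

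**What limits selection.** The MoCA, AD8, CDR and FAQ cut-offs are the same in both arms. Data Analysis compares baseline characteristics by arm, adds as covariates the relevant variables that differ, and controls in particular for sex, comorbidities and cognitive impairment. Hypotheses are tested through the group-by-time interaction.

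**What is not there.** The text sets no consecutive or random order of approach, no screening log and no recruiter blind to arm. The only blinding stated is of the evaluators who complete the environment and policy assessments.

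**The concern.** Randomising hospitals balances, in expectation, the patients admitted to them. It does not balance the patients enrolled if enrolment depends on choices made by people who know the arm. Here those choices come after allocation, and after a training period chosen because staff behaviour is expected to have changed by its end. A staff member in an FFC-AC-EIT hospital could, without any intent, put forward patients who seem likely to respond, while an EO colleague has no such picture in mind. With far more eligible patients than places, there is room for this.

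At stake is the comparability of the arms. Enrolling more patients would not reduce such a bias, and covariates can correct only for what is measured.

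**Working it through.** **1. The plan's own recruitment figures.** 50 patients / 10 months = 5.0 per month, as stated. 12 hospitals x 50 = 600, as stated. With 52/12 weeks per month, 10 months is 43.3 weeks, and 50 / 43.3 = 1.15 per week, inside the stated 1-2 per week.

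**2. Share of eligible patients enrolled.** The 7 to 8 eligible per week is read as per hospital, because the 50 patients and 5 per month beside it are per hospital.
- At 7 per week: 7 x 43.3 = 303 eligible; 50 / 303 = 16.5%.
- At 8 per week: 8 x 43.3 = 347 eligible; 50 / 347 = 14.4%.
- With 4.0 to 4.5 weeks per month, the range widens to 13.9-17.9%.

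**3. Does the staff member know the arm?** The two conditions look different from inside a hospital. FFC-AC-EIT units have champions, a facilitator working 10 hours weekly for two months and then four hours weekly, monthly stakeholder meetings, weekly emails and a supplies voucher. EO units have in-service education and no further contact. No concealment is described. Knowledge of the arm is therefore a strong inference, but it is not stated.

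**4. Upper bound on the shift.** This is an illustration; the model and the correlations are assumptions and are not in the documents. Suppose that in one arm the enrolled fraction p is the top p of a normally distributed staff preference that correlates r with an outcome, and that in the other arm enrolment is random. The enrolled mean then shifts by r x phi(z)/p SD, where phi is the standard normal density and z its upper-p cut-off.
- p = .165: phi(.975)/.165 = .248/.165 = 1.50.
- p = .144: phi(1.062)/.144 = .227/.144 = 1.57.

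| r | Shift, p = .165 | Shift, p = .144 |
|---|---|---|
| .05 | 0.08 SD | 0.08 SD |
| .10 | 0.15 SD | 0.16 SD |
| .15 | 0.23 SD | 0.24 SD |

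This treats every eligible patient who is not enrolled as a staff choice. If random refusal or non-contact accounts for part of the gap, so that staff select 37.5% or 60% of eligible patients (assumed values), phi(z)/p falls to 1.01 or 0.64, and the shift at r = .10 falls to 0.10 or 0.06 SD. If staff report all eligible patients, their contribution is zero.

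**5. What reaches the planned test.** A shift in function present at admission and fully persisting drops out of the group-by-time term. If only .60 of it persists (the repeated-measures correlation in Sample Size, borrowed as an assumption), a 0.15 SD admission shift becomes 0.60 x 0.15 = 0.09 SD later. The change then differs by 0.09 - 0.15 = -0.06 SD, against the arm that enrolled better-functioning patients. Length of stay and in-hospital falls have no pre-enrolment value to subtract, so a shift in them passes straight into the comparison. Selection on expected trajectory also survives, because it enters the change itself.

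**The case against.** The strongest reply is that the room for staff choice may be small. The 1-2 per week is based on past recruitment and reads as an expected yield: refusal, the 48-hour limit, the need for a contactable caregiver and consent through a representative can all fall between eligible and enrolled. This stands, and it is why step 4 gives an upper bound. It does not close the gap, because no rule governs who fills the weekly places.

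A reader might set the 0.15 or 0.23 SD shift against the planned Barthel effect of d = .24 and infer that selection could account for most of it. The documents do not support that: Barthel is measured at admission and tested by group-by-time, where a stable shift largely cancels. Nor do they support saying that every outcome is biased, or that staff are known to be aware of the arm.

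The safeguards are real but partial. Common cut-offs limit who may enter, not which eligible patients are approached, and three of the four scales are completed by an informant. Covariates reach measured differences only. The assurance of similar recruitment across settings rests on the enrolment rate, not on how patients are chosen. FFC-AC-EIT is delivered to the whole unit, and no site incentive is tied to who is enrolled. That lessens any motive but does not remove discretion.

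The plan also refers to a Human Subjects section that is not supplied. It is cited for consent, but recruitment detail there cannot be excluded.

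**Conclusion.** The concern holds in a limited form: as written, the plan leaves selection after randomisation open, so the arms can differ in who is enrolled. The documents do not show that they will. Identification after allocation, an enrolled share of about 14-17% and the lack of a rule for approach follow from the text, if 7 to 8 per week is per hospital. Staff knowledge of the arm is inferred.

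The exposure is greatest for length of stay, in-hospital falls and selection on expected trajectory, and much smaller for a stable difference in admission function. The 0.08 to 0.23 SD range is an upper bound for correlations of .05 to .15, with one-arm selection and all non-enrolment due to staff. The realised size is unknown. The plan should be changed before recruitment, because the analysis cannot fully repair a selection difference.

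**What to change.** In the recruitment paragraph under Patient Participants, have the designated staff member supply the complete list of unit patients who meet the criteria that can be checked from the chart: age 65 or over, on the unit 48 hours or less, and no listed exclusion. The staff member does not judge suitability. Research staff then approach the listed patients in a computer-generated random order until the weekly target is met. Keep a log of patients listed, approached, eligible and consented, and report it by arm.

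This needs protocol wording, a random-order list and a log; design and sample size do not change. The cost is some added list handling and some added screening of patients who prove ineligible, since the MoCA and the informant scales come after listing. It should fit within the existing recruitment effort, but the plan does not say who screens, so that role should be named.
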